5.1.2 Determination of Sample Size

The sample size for stage 1 is determined empirically.

Stage 1: Stage 1 will have up to 63 patients and approximately 10 cohorts (Cohorts 1 to 6D). The anticipated numbers of patients per cohort are 3 for Cohort 1; 4 each for Cohorts 2, 6C, and 6D; and 8 each for Cohorts 3 through 6B.

5.2 Changes in the Conduct of the Study or Planned Analyses

5.2.1 Changes in the Conduct of the Study

Not applicable.

5.2.2 Changes to Analyses Prior to Database Lock

The definition of modified intent-to-treat (mITT) population is changed to all randomized patients who have baseline and at least 1 postbaseline assessment for 1 or more of the exploratory efficacy measurements from all patients who receive study treatment and have baseline and at least 1 postbaseline assessment for 1 or more of the exploratory efficacy measurements.

6. Data Handling and Analysis Conventions

6.1 Study Treatment Conventions

6.1.1 Analysis Days

Treatment days are defined as shown in [Table 6-1](#).

Table 6-1 Analysis Day Definitions

Term	Description
Treatment Day	Relative to treatment start date If analysis date \geq treatment start date: 
 • Day = analysis date – treatment start date + 1 
 ○ Day 1 = treatment start date If analysis date < treatment start date: 
 • Day = analysis date – treatment start date 
 ○ Day -1 = day before treatment start date ○ There is no Day 0

6.2 Analysis Visit Windows

All stage 1 analyses will be performed based on the analysis visit windows defined below.

The analysis visit windows for exploratory efficacy and safety endpoints follow the schedule of visits in the protocol and are defined as follows:

6.2.1 Treatment Cycle 1

Table 6-2 Analysis Visit Definitions 1

Analysis Phase	Analysis Visit (Derived)	Target Number of Days from Treatment	Window ^a
Pretreatment	Study Baseline	Day 1	Treatment Day 1
Treatment	Day 2	Day 2	Treatment Day [2, 4]
	Week 1	Day 7	Treatment Day [5, 10]
	Week 2	Day 14	Treatment Day [11, 20]
	Week 4	Day 28	Treatment Day [21, 41]
	Week 8	Day 56	Treatment Day [42, 69]
	Week 12	Day 84	Treatment Day [70, 125]
	Week 24	Day 168	Treatment Day \geq 126

For endpoints with scheduled visits of Study Baseline (Day 1), Day 2, Week 1, Week 2, Week 4, Week 8, Week 12, and Week 24.

^a Study days are calculated based on the visit date – Treatment (Day 1) visit date + 1.

Table 6-3 Analysis Visit Definitions 2

Analysis Phase	Analysis Visit (Derived)	Target Number of Days from Treatment	Window ^a
Pretreatment	Study Baseline	Day 1	Treatment Day 1
Treatment	Week 4	Day 28	Treatment Day [2, 41]

Analysis Phase	Analysis Visit (Derived)	Target Number of Days from Treatment	Window ^a
	Week 8	Day 56	Treatment Day [42, 69]
	Week 12	Day 84	Treatment Day [70, 125]
	Week 24	Day 168	Treatment Day >=126

For endpoints with scheduled visits of Study Baseline (Day 1), Week 4, Week 8, Week 12, and Week 24.

^a Study days are calculated based on the visit date – Treatment (Day 1) visit date + 1.

Table 6-4 Analysis Visit Definitions 3

Analysis Phase	Analysis Visit (Derived)	Target Number of Days from Treatment	Window ^a
Pretreatment	Study Baseline	Day 1	Treatment Day 1
Treatment	Week 1	Day 7	Treatment Day [2, 31]
	Week 8	Day 56	Treatment Day [32, 69]
	Week 12	Day 84	Treatment Day [70, 125]
	Week 24	Day 168	Treatment Day >=126

For endpoints with scheduled visits of Study Baseline (Day 1), Week 1, Week 8, Week 12, and Week 24.

^a Study days are calculated based on the visit date – Treatment (Day 1) visit date + 1.

Table 6-5 Analysis Visit Definitions 4

Analysis Phase	Analysis Visit (Derived)	Target Number of Days from Treatment	Window ^a
Pretreatment	Study Baseline	Day 1	Treatment Day 1
Treatment	Week 1	Day 7	Treatment Day [2, 31]
	Week 8	Day 56	Treatment Day [32, 111]
	Week 24	Day 168	Treatment Day >=112

For endpoints with scheduled visits of Study Baseline (Day 1), Week 1, Week 8, and Week 24.

^a Study days are calculated based on the visit date – Treatment (Day 1) visit date + 1.

Table 6-6 Analysis Visit Definitions 5

Analysis Phase	Analysis Visit (Derived)	Target Number of Days from Treatment	Window ^a
Pretreatment	Study Baseline	Day 1	Treatment Day 1
Treatment	Week 4	Day 28	Treatment Day [2, 55]
	Week 12	Day 84	Treatment Day [56, 125]
	Week 24	Day 168	Treatment Day >=126

For endpoints with scheduled visits of Study Baseline (Day 1), Week 4, Week 12, and Week 24.

^a Study days are calculated based on the visit date – Treatment (Day 1) visit date + 1.

Table 6-7 Analysis Visit Definitions 6

Analysis Phase	Analysis Visit (Derived)	Target Number of Days from Treatment	Window ^a
Treatment	Week 8	Day 56	Treatment Day [2, 69]
	Week 12	Day 84	Treatment Day [70, 125]
	Week 24	Day 168	Treatment Day \geq 126

For endpoints with scheduled visits of Week 8, Week 12, and Week 24.

^a Study days are calculated based on the visit date – Treatment (Day 1) visit date + 1.

Table 6-8 Analysis Visit Definitions 7

Analysis Phase	Analysis Visit (Derived)	Target Number of Days from Treatment	Window ^a
Pretreatment	Study Baseline	Day 1	Treatment Day 1
Treatment	Week 12	Day 84	Treatment Day [2, 125]
	Week 24	Day 168	Treatment Day \geq 126

For endpoints with scheduled visits of Study Baseline (Day 1), Week 12, and Week 24.

^a Study days are calculated based on the visit date – Treatment (Day 1) visit date + 1.

Table 6-9 Analysis Visit Definitions 8

Analysis Phase	Analysis Visit (Derived)	Target Number of Days from Treatment	Window ^a
Pretreatment	Study Baseline	Day 1	Treatment Day 1
Treatment	Week 24	Day 168	Treatment Day \geq 2

For endpoints with scheduled visits of Study Baseline (Day 1), and Week 24.

^a Study days are calculated based on the visit date – Treatment (Day 1) visit date + 1.

6.2.2 Treatment Cycle 2

Table 6-10 Analysis Visit Definitions 1 (Retreatment)

Analysis Phase	Analysis Visit (Derived)	Target Number of Days from Retreatment	Window ^a
Pre-retreatment	Cycle Baseline	Day 1	Retreatment Day 1 (Week 12 from treatment start)
Retreatment	Day 1R	Day 2	Treatment Day [2, 4]
	Week 1R	Day 7	Treatment Day [5, 17]
	Week 4R	Day 28	Treatment Day [18, 41]
	Week 8R	Day 56	Treatment Day [42, 69]
	Week 12R	Day 84	Treatment Day \geq 70

For endpoints with scheduled visits of Cycle Baseline (Day 1), Day 1R, Week 1R, Week 4R, Week 8R, and Week 12R.

^a Study days from retreatment are calculated based on the visit date – retreatment visit date + 1.

Table 6-11 Analysis Visit Definitions 2 (Retreatment)

Analysis Phase	Analysis Visit (Derived)	Target Number of Days from Retreatment	Window^a
Pre retreatment	Cycle Baseline	Day 1	Retreatment Day 1 (Week 12 from treatment start)
Retreatment	Week 4R	Day 28	Treatment Day [2, 41]
	Week 8R	Day 56	Treatment Day [42, 69]
	Week 12R	Day 84	Treatment Day \geq 70

For endpoints with scheduled visits of Cycle Baseline (Day 1), Week 4R, Week 8R, and Week 12R.

^a Study days from retreatment are calculated based on the visit date – retreatment visit date + 1.

Table 6-12 Analysis Visit Definitions 3 (Retreatment)

Analysis Phase	Analysis Visit (Derived)	Target Number of Days from Retreatment	Window^a
Pre retreatment	Cycle Baseline	Day 1	Retreatment Day 1 (Week 12 from treatment start)
Retreatment	Day 1R	Day 2	Treatment Day [2, 42]
	Week 12R	Day 84	Treatment Day \geq 43

For endpoints with scheduled visits of Cycle Baseline (Day 1), Day 1R, and Week 12R.

^a Study days from retreatment are calculated based on the visit date – retreatment visit date + 1.

Table 6-13 Analysis Visit Definitions 4 (Retreatment)

Analysis Phase	Analysis Visit (Derived)	Target Number of Days from Retreatment	Window^a
Pre retreatment	Cycle Baseline	Day 1	Retreatment Day 1 (Week 12 from treatment start)
Retreatment	Week 8R	Day 56	Treatment Day [2, 69]
	Week 12R	Day 84	Treatment Day \geq 70

For endpoints with scheduled visits of Cycle Baseline (Day 1), Week 8R, and Week 12R.

^a Study days from retreatment are calculated based on the visit date – retreatment visit date + 1.

Table 6-14 Analysis Visit Definitions 5 (Retreatment)

Analysis Phase	Analysis Visit (Derived)	Target Number of Days from Retreatment	Window^a
Pre retreatment	Cycle Baseline	Day 1	Retreatment Day 1 (Week 12 from treatment start)
Retreatment	Week 4R	Day 28	Treatment Day [2, 55]
	Week 12R	Day 84	Treatment Day \geq 56

For endpoints with scheduled visits of Cycle Baseline (Day 1), Week 4R, and Week 12R.

^a Study days from retreatment are calculated based on the visit date – retreatment visit date + 1.

Table 6-15 Analysis Visit Definitions 6 (Retreatment)

Analysis Phase	Analysis Visit (Derived)	Target Number of Days from Retreatment	Window ^a
Pre retreatment	Cycle Baseline	Day 1	Retreatment Day 1 (Week 12 from treatment start)
Retreatment	Week 12R	Day 84	Treatment Day ≥ 2

For endpoints with scheduled visits of Cycle Baseline (Day 1), and Week 12R.

^a Study days from retreatment are calculated based on the visit date – retreatment visit date + 1.

The following general conventions will apply unless otherwise specified:

- If both scheduled and unscheduled visits occur within a single window, the scheduled visit will be used; unscheduled visits will be used only if there is no scheduled visits available in that window. If multiple visits are eligible for windowing within a single visit window, the visit closest to the target day will be used in the analysis. If multiple visits are equidistant to the target day, the latest visit will be used.
- For clinical laboratory variables, the latest nonmissing assessment within any analysis window will be flagged as the analysis value. This rule will be applied separately for each variable for nonmissing data only. (The exception is because re-runs of laboratory variables may only involve one or a few variables and would thus include missing data for many variables)
- All assessments will be included in respective listings.

6.3 Missing/Incomplete Date Conventions

Dates may be imputed with year, month, and day values under certain scenarios:

Table 6-16 Imputation Scenarios

Scenario	Complete			Imputable
	Year	Month	Day	
1	Yes	Yes	Yes	Complete
2	Yes	Yes	—	Yes
3	Yes	—	Yes	No ^a
4	Yes	—	—	Yes
5	—	Yes	Yes	No ^a
6	—	Yes	—	No ^a
7	—	—	Yes	No ^a
8	—	—	—	Yes

^a Not allowed per database design.

Dates will be imputed initially toward a specified target date for imputable scenarios 2, 4, and 8, and adjusted against the latest reasonable dates. The initial imputed date is determined by the algorithm show in [Table 6-17](#).

Table 6-17 Initial Imputed Date Algorithm

Available Year (YYYY)	Available Month (MM)			
	Missing	< Target Month	= Target Month	> Target Month
Missing	Target Date	—		
< Target Year	YYYY-12-31	YYYY-MM-LD		
= Target Year	Target Date	YYYY-MM-LD	Target Date	YYYY-MM-01
> Target Year	YYYY-01-01	YYYY-MM-01		

YYYY = available start date year; MM = available start date month; LD = last day of the month.

6.3.1 Missing/Incomplete AE Start Date

AE start dates will be imputed as the minimum of the following:

- Initial imputed date, where target date = treatment start date
- Complete end date

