8.2 Washout Intervals/Run-in

For patients not on RESTASIS at the screening visit, there will be a 2-week run-in period with REFRESH PLUS, for use 4 times per day. If patients are using topical RESTASIS at screening, their screening period will be extended to a 13-week period to allow for washout of topical RESTASIS in conjunction with the 2-week run-in with REFRESH PLUS. Any screening diagnostic procedures that were performed at the start of the extended screening period will be repeated within days -14 to -2.

Approval Date: 19-Jan-2017

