8.12 Definitions

8.12.1 Adverse Event

An adverse event is any untoward medical occurrence in a patient or clinical investigation subject administered a pharmaceutical product and that does not necessarily have a causal relationship with this treatment. An adverse event can therefore be any unfavorable and unintended sign (including an abnormal laboratory finding), symptom, or disease temporally associated with the use of a medicinal (investigational) product, whether or not related to the medicinal (investigational) product. In addition, during the screening period, adverse events will be assessed regardless of the administration of a pharmaceutical product.

Note: Adverse events must be collected once informed consent has been obtained, regardless of whether or not the patient has been administered study drug.

Progression of treatment indication including new or worsening of anticipated clinical signs or symptoms, which are collected as clinical efficacy variables and assessed as unequivocally associated with the disease progression and/or lack of efficacy, should NOT be reported as adverse events unless the disease progression is greater than anticipated in the natural course of the disease.

Adverse events will be assessed, documented, and recorded in the eCRF throughout the study (ie, after informed consent has been obtained). At each visit, the investigator will begin by querying for adverse events by asking each patient a general, non-directed question such as “How have you been feeling since the last visit?” Directed questioning and examination will then be done as appropriate. All reported adverse events will be documented on the appropriate eCRF.

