5.1.1.4.2 Adverse Events

Adverse events (AEs) are defined as shown in [Table 5-17](#).

Table 5-17 AE Terms

Term	Description
TEAE	An adverse event recorded on the eCRF would be considered treatment-emergent if either of the following conditions are met: AE onset date \geq first study treatment date; or AE onset date $<$ first study treatment date and either: 
 • the severity of the event worsened on or after the first study treatment date, or • the event became serious on or after the first study treatment date
SeriousTEAE	An event identified as TEAE that further meets SAE criteria at any time would be a serious TEAE.

SAE = serious adverse event; TEAE = treatment-emergent adverse event

AEs, encompassing abnormalities and surgeries reported as occurring after the Screening Visit, will be coded using MedDRA version 19.0 or newer. Unique patients reporting AEs in the following AE categories will be summarized by treatment group for the safety population as shown in [Table 5-18](#).

Table 5-18 AE Summaries

Parameter	Description	Timing	Methodology
Overall summary	Overall summary for the following categories: 
 • TEAEs (ocular vs. non-ocular) • Study drug-related TEAEs (ocular vs. non-ocular) • Study procedure-related TEAEs (ocular vs. non-ocular) • Serious TEAEs (ocular vs. non-ocular) • TEAEs leading to study 	From treatment start date until Week 24/Week 12R or early termination date, whichever comes first	Categorical descriptives

Parameter	Description	Timing	Methodology
	
discontinuation (ocular vs. non-ocular)
 
 Deaths 		
TEAEs ^a	
Overall summary and by SOC in alphabetical order, PT and worst severity
 
The worst severity is defined as the greater of the onset severity and maximum severity following onset recorded on the eCRF. If the same TEAE term has been reported more than once for a subject with different severity grades, the worst severity grade will be used in the tabulation.
	
From treatment start date until Week 24/Week 12R or early termination date, whichever comes first
	Categorical descriptives

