6.3.3 Missing/Incomplete AE/Medication End Date

AE and medication end dates will be imputed as the minimum of the following:

- Initial imputed date, where target date = from treatment start date until Week 24/Week 12R or early termination date, whichever comes first
- Death date

		
---	--	---

[REDACTED]

[REDACTED]

[REDACTED]

[REDACTED]	[REDACTED]	[REDACTED]
[REDACTED]	[REDACTED]	[REDACTED]
[REDACTED]	[REDACTED]	[REDACTED]
[REDACTED]	[REDACTED]	[REDACTED]

[REDACTED]

[REDACTED]

[REDACTED]	[REDACTED]	[REDACTED]
[REDACTED]	[REDACTED]	[REDACTED]
[REDACTED]	[REDACTED]	[REDACTED]

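### SAP 6.3.1 limits an imputed AE start date only by a complete end date, so an event whose partial end date already precedes treatment can be dated to Day 1 and counted as a TEAE

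*SAP*

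**What the plan says.** SAP 6.3.1 states "AE start dates will be imputed as the minimum of the following" and lists two terms: "Initial imputed date, where target date = treatment start date" and "Complete end date". The first term comes from Table 6-17. That table returns the target date when the start is wholly missing, and also when only the year is known and it equals the treatment year.

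SAP Table 6-16 sets out which partial dates may occur. It uses the label Complete for one pattern only, with year, month and day all present. Dates lacking a day, dates with a year only and wholly missing dates are allowed and can be imputed.

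End dates have their own rule in SAP 6.3.3: "AE and medication end dates will be imputed as the minimum of the following", the terms being a Table 6-17 date and the death date. Nothing in 6.3 requires the imputed start to fall on or before the imputed end.

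SAP Table 5-17 defines a TEAE: "An adverse event recorded on the eCRF would be considered treatment-emergent if either of the following conditions are met". The first condition is an onset on or after the first treatment date.

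Pretreatment events are in scope. Protocol 8.12.1 says "Adverse events must be collected once informed consent has been obtained, regardless of whether or not the patient has been administered study drug". The pretreatment period is normally a 2-week run-in, but for patients using topical RESTASIS at screening, "their screening period will be extended to a 13-week period" (Protocol 8.2).

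**The concern.** The cap in 6.3.1 exists to stop an event that ended before treatment from being given an onset on Day 1. It does this when the end date is complete. When only the end month or year is recorded, the cap does not apply, even where that month or year rules out any overlap with treatment. The imputed onset then contradicts the recorded data, and the separately imputed end date falls before the start date.

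At stake is a false count in the TEAE tables, the main safety summary of Stage 1. Cohorts have 3, 4 or 8 patients, so one extra patient is visible.

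**Working it through.** The documents give no figure on this point, so the check applies the rules to example records. The calendar dates are illustrative assumptions.

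**Inputs.** Start rule: SAP 6.3.1 with Table 6-17. End rule: SAP 6.3.3 with Table 6-17. TEAE test: Table 5-17. Pretreatment period: Protocol 8.2. Cohort sizes: SAP 5.1.2. Counting rule: Table 5-2.

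**Which records can arise.** The SAP treats what occurred before the Screening Visit as history (5.1.1.2.5) and what occurred after it as AEs (5.1.1.4.2). The event must therefore end inside the screening period.

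- Extended screening, treatment 15 Mar 2016: 13 weeks is 91 days, which goes back to 15 Dec 2015. All of February 2016 lies inside.
- 2-week run-in, treatment 15 Mar 2016: Day -14 is 1 Mar 2016. A February end precedes screening, so the record would not be an AE.
- 2-week run-in, treatment 5 Mar 2016: Day -14 is 20 Feb 2016. An end between 20 and 29 Feb lies inside.

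With the 2-week run-in, then, the case arises only when the window crosses a month boundary.

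**Applying the rules.** Start as written = min(Table 6-17 date, complete end date if there is one). Start with the fix = min(Table 6-17 date, latest date consistent with the end date).

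| Treatment | AE start | AE end | Start as written | TEAE | End date | Start with fix | TEAE |
|---|---|---|---|---|---|---|---|
| 15 Mar 2016 (13-week) | missing | Feb 2016 | 15 Mar 2016 | yes | 29 Feb 2016 (imputed) | 29 Feb 2016 | no |
| 15 Mar 2016 (13-week) | 2016 only | Feb 2016 | 15 Mar 2016 | yes | 29 Feb 2016 (imputed) | 29 Feb 2016 | no |
| 15 Mar 2016 (13-week) | missing | 2015 only | 15 Mar 2016 | yes | 31 Dec 2015 (imputed) | 31 Dec 2015 | no |
| 5 Mar 2016 (2-week) | missing | Feb 2016 | 5 Mar 2016 | yes | 29 Feb 2016 (imputed) | 29 Feb 2016 | no |
| 15 Mar 2016, control | missing | 20 Feb 2016 | 20 Feb 2016 | no | 20 Feb 2016 (recorded) | 20 Feb 2016 | no |
| 15 Mar 2016, control | Feb 2016 | Feb 2016 | 29 Feb 2016 | no | 29 Feb 2016 (imputed) | 29 Feb 2016 | no |
| 15 Mar 2016, control | missing | Mar 2016 | 15 Mar 2016 | yes | 31 Mar 2016 (imputed) | 15 Mar 2016 | yes |

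The target date in 6.3.3 is worded as a span rather than a single date. This does not affect the February or 2015 ends: any target on or after treatment start gives the last day of the recorded month or year.

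The first two controls show that the rule works when the end date is complete or when an earlier start month is recorded. The third shows that an ambiguous date stays a TEAE under the fix.

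**Size.** One extra patient in a row adds 1/4 = 25 points, 1/8 = 12.5 points, or 1/3 = 33 points in Cohort 1. Table 5-2 counts a patient once per category, so these are maxima: the addition is zero in any row where the patient already has a qualifying event.

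**The case against.** The best counter-reading is the general sentence in SAP 6.3: "Dates will be imputed initially toward a specified target date for imputable scenarios 2, 4, and 8, and adjusted against the latest reasonable dates". On this view a start after the known end month is not reasonable and would be corrected. However, the only adjustment that 6.3.1 specifies for AE starts is the complete end date, and Table 6-16 reserves that label for full dates. A programmer following the text would build the fault. If the sponsor meant the imputed end date, the text should say so.

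It is also fair to say that moving an unknown onset toward treatment is a deliberate safety convention. That stands wherever timing really is unknown. It does not cover records whose end month or year already excludes treatment.

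Several mitigating points stand. AEs are asked about at every visit, so a start without a usable month together with an end without a day should be uncommon. Stage 1 summaries are descriptive. Listings show partial dates as recorded and include pretreatment AEs (SAP 5.1.1.1.4, 6.7 and the Table 5-18 footnote), so a careful reader could spot the contradiction.

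Three stronger readings are tempting but unsupported:

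- **That a large share of screening events would be misclassified.** If the end day is uniform over the last 14 or 91 days before treatment, it falls in an earlier calendar month about 25% (roughly 7.5/30.4) or 84% (roughly 1 - 14.7/91) of the time. These figures presuppose a pretreatment AE with a month-only end and no usable start. They are not error rates.
- **That the rule wrongly attributes events to the drug by up to 33 points.** The 33-point figure belongs to Cohort 1, which receives vehicle and sham and no active drug.
- **That such an event automatically becomes Severe and Related.** Table 6-21 applies only when those fields are also blank, and the SAP does not say that the period is assigned from the imputed onset. The effect follows only if both conditions hold.

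**Conclusion.** The point holds as a narrow, minor fault in a stated rule. It needs two things on one record: a start that is wholly missing or known only to the treatment year, and an end without a day whose recorded month or year lies before treatment. (A start recorded to the treatment month with an earlier end month also triggers it, but that is a data error for query.) When both are present, 6.3.1 gives an onset that the eCRF contradicts, and Table 5-17 counts the event as a TEAE.

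The number of such records cannot be derived from the documents. The assumption here is 0 to 2 in Stage 1, so no effect at all is within the range. Patients in the 13-week extended screening are the more likely source. The largest effect of one record is 25 or 12.5 points in an active cohort's TEAE row. Severity and relationship rows could be affected only under the further conditions on Table 6-21 given above.

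**What to change.** Replace the second term of SAP 6.3.1 with: *End date, where a partial end date is first set to the latest date consistent with it (YYYY-MM-LD, or YYYY-12-31 if only the year is known).*

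This changes only records whose end month or year rules out the imputed start. An end in the treatment month or later, or an end known only to the treatment year or later, keeps the current imputation to Day 1. The cost is one line in the SAP and one in the date-imputation program, with no new data.
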